**METHODS:** The study is a randomized clinical trial with repeated measurements. A convenient sample of 72 adults who were treated with anticoagulants for atrial fibrillation was recruited from two teaching hospitals in northern Taiwan. Participants were randomly assigned 1:1 to either the control group (n = 36) or the intervention group (n = 36) after completion of baseline questionnaires. Allocation was balanced by site by using a minimization method. The health belief model based self-management intervention comprised two main components: a 60-minute individual face-to-face instruction and six follow-up telephone calls. Participants in the control group received regular medication education, 10-minute individual instruction for health knowledge and six follow-up telephone calls for concerning health. Data were collected at baseline, third month, and sixth month in both groups, by using self-administered questionnaires. The investigator administered the study questionnaire after obtaining informed consent from each subject. The data collection took place at the waiting areas outside the outpatient clinics during the patients' visits to the clinics. For subjects who were unable to read the questionnaire due to vision or other problems, the investigator read each question to help them complete the questionnaire. The instruments include the Atrial Fibrillation Knowledge Scale, Satisfaction Scale about Service and Warfarin Treatment, Belief about Anticoagulation Survey, and Self-Efficacy for Appropriate Medication Use Scale.

**DATA ANALYSIS:** Data were analyzed using the Statistical Package for Social Sciences 20.0 (SPSS, Inc., Chicago, IL, USA). Descriptive analyses were used to describe study variables. Independent t-tests and one-way analysis of variance (ANOVA) were performed to analyze the baseline equivalent between study groups. The generalized estimating equations were used to analyze the efficacy of the intervention for enhancing knowledge, knowledge, perceived benefits, perceived barriers, self-efficacy, and adherence to anticoagulant therapies in patients treated with oral anticoagulants for atrial fibrillation.

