## Participant Flow Template

Recruitment Details	Patients with AFib were recruited from the cardiology clinics of two general hospitals in northern Taiwan. Potential participants were referred by cardiologists and screened by one of the investigators to determine their eligibility
[*] Pre-assignment Details	

Period ①		①		
*	Overall Study	EG	CG	
	*	Intervention Group	Control Group	
	*§ Arm/Group	Number of Participants ④	Number of Participants ④	Number of Participants
	* Started	36	36	
	[*] Milestone			
	[*] Milestone			
	[*] Milestone			
	* Completed	33	30	
	Not Completed	(automatically calculated)		
	Reason Not Completed Type ③			
	[*] Adverse Event			
	[*] Death			
	[*] Lack of Efficacy			
	[*] Lost to			
	[*] Physician			
	[*] Pregnancy			
	[*] Protocol			
	[*] Withdrawal by	1	2	
	[*] Other Change Medication	1	2	
	[*] Other Operation	1	0	

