## Outcome Measure Template

	Primary	Secondary	Other Pre-specified	Post-Hoc
* Outcome Measure	(Select One)			
* Outcome Measure	Anticoagulant medication adherence			
* Outcome Measure	Participants were monitor for up to 24 weeks, These is the score of participants who had been monitor for medication adherence. The study adapted Adherence to Refills Medications Scale (ARMS) assess the participants' medication adherence when taking anticoagulants			
Description	Ups to 24 weeks			
* Outcome Measure Time	Ups to 24 weeks			

More details available in the Results Data Element Definitions. April 2017

* Measure Type (Select One)	* Measure of (Select One)	EG		CG			
* Row/Category Title	* Row/Category Title						
* § Arm/Group Description		Intervention group		Control group			
* Number of Participants Analyzed	[*] Analysis: Population	36		36			
All participants with baseline and at least fellow up for 24 weeks							
Count of Participants ③	Not Applicable ④						
Mean	Standard deviation						
Median	Standard Error						
Least Squares Mean	Inter-Quartile Range						
[*] Row/Category Title	Medication adherence	8.1	1.4	9.2	2.2		③ ④
[*] Row/Category Title			③ ④		③ ④		③ ④
* Unit of	score						

*Statistical Analysis Template*

Statistical Analysis Overview	* Comparison Group Selection ①	 ✓ Arm/Group 1	 ✓ Arm/Group 2	 Arm/Group 3
	Comments ②			
	* Type of Statistical Test	(Select One) Superiority Non-inferiority Equivalence Other (for example, single group or other descriptive analysis)		
	[*] Comments ③			
Statistical Test of Hypothesis	[*] P-Value (if applicable)	0.05 [calculated value, not the a priori threshold for statistical significance]		
	Comments ②			
	[*] Method (required if p-value entered)	(Select One) ANCOVA ANOVA Chi-Squared Chi-Squared, Corrected Cochran-Mantel-Haenszel	Fisher Exact Kruskal-Wallis Log Rank Mantel-Haenszel McNemar	Mixed Models Analysis Regression, Cox Regression, Linear Regression, Logistic Sign Test t-Test, 1-Sided F-Test, 2-Sided Wilcoxon (Mann-Whitney) Other ( )
	Comments ②			

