Method of Estimation	[*] Estimation Parameter (if applicable)	(Select One) Cox Proportional Hazard Hazard Ratio (HR) Hazard Ratio, Log	Mean Difference (Net) Median Difference (Final Values) Median Difference (Net) (generalized estimating equation) Odds Ratio (OR)	Odds Ratio, Log Risk Difference (RD) Risk Ratio (RR) Risk Ratio, Log
	Estimated Value	0.5 (calculated value)		
	Confidence Interval (if applicable)	Level: 95 % Confidence Interval	Number of Sides: (Select One) 2-sided	1-sided
	Parameter Dispersion	Lower Limit: _____	Upper Limit: _____	Type: (Select One) Standard Deviation Standard Error of the Mean
	Estimation Comments ②			
Other Statistical Analysis ④	A generalized estimating equation (GEE) 28 was used to model each outcome variable as a function of group effect, time effect, and group by time interaction effect.			

\* Required [\*] Conditionally required

- ① Use the checkboxes to select the Arms/Groups (pre-populated from the Outcome Measure) involved in the statistical analysis.
- ② (Optional) Include any relevant information about the row above (e.g., the null hypothesis, details of the power calculation, adjustment for multiple comparisons, the *a priori* threshold for statistical significance, the direction of the comparison). Do not include written results or conclusions.
- ③ If a non-inferiority or equivalence analysis, information on the definition of the non-inferiority or equivalence margin is required.
- ④ If the statistical analysis cannot be submitted using the Statistical Test of Hypothesis or Method of Estimation options, provide a description and the results

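### The stated GEE omits site, the factor used to balance allocation; intervals are somewhat too wide when levels (group comparisons) or changes over time (group-by-time) differ by site

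*Combined protocol and SAP*

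**What the plan says.** Study Protocol, METHODS: patients were "recruited from two teaching hospitals in northern Taiwan" and "randomly assigned 1:1 to either the control group (n = 36) or the intervention group (n = 36"). The balancing factor is named once: "Allocation was balanced by site by using a minimization method". No other factor is mentioned. On timing, "Data were collected at baseline, third month, and sixth month in both groups".

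Study Protocol, DATA ANALYSIS: "The generalized estimating equations were used to analyze the efficacy of the intervention", with no covariates listed.

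Outcome Measure Template, Other Statistical Analysis: GEE is used to "model each outcome variable as a function of group effect, time effect, and group by time interaction effect". This is the only explicit model.

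No site-adjusted, stratified or sensitivity analysis by site appears. The documents do not say which coefficient is the efficacy test. They give no sample-size calculation, working correlation or site-level figures.

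**The concern.** Balancing the arms within each hospital removes between-hospital variation from the true sampling error of the treatment comparison. A model without site does not know this. It leaves that variation in the residual and so in the estimated standard error. Intervals come out too wide and the test rejects less often than its nominal level.

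What is at stake is precision. The trial has 72 patients, of whom 63 completed (33 and 30 in the Participant Flow Template), and states no power, so precision is worth keeping. The same model serves every outcome. One instrument is a satisfaction scale that covers service, which could plausibly vary by hospital, although the documents do not show that it does.

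**Working it through.** **Inputs from the documents.** Two sites; 36 per arm; three visits; model terms group, time and group-by-time; completers 33 and 30; adherence SDs 1.4 and 2.2 ("Medication adherence 8.1 1.4 9.2 2.2"), pooled √((1.4² + 2.2²)/2) = 1.84, used only to scale one check. The plan has no power figure to reproduce.

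**Assumptions.** Within-site SD 1 at each visit; within-patient correlation 0.5; effect 0.6 SD; exact balance within site; two-sided 5% (no threshold is stated in advance); site gap *d* varied; share of patients in the smaller site *p*, first set to 0.5.

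**Change contrast, closed form.** The within-site variance of a change is 2(1 − 0.5) = 1. The true SE is √(2 × 1/36) = 0.236, with or without site in the model. If a gap *d* opens after baseline, the model without site sees variance 1 + *d*²*p*(1 − *p*).

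- SE estimated without site = √(2[1 + *d*²*p*(1 − *p*)]/36)
- Power without site = Φ((0.6 − 1.96 × that SE)/0.2357)
- Power with site = Φ(0.6/0.2357 − 1.96) = 72.1%

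| Site gap | SE without site | Ratio to true SE | Null rejection | Power without → with site |
|---|---|---|---|---|
| constant over time | 0.236 | 1.00 | 5.0% | 72.1% → 72.1% |
| 0.5 SD at follow-up | 0.243 | 1.03 | 4.3% | 70.0% → 72.1% |
| 1.0 SD at follow-up | 0.264 | 1.12 | 2.8% | 63.8% → 72.1% |

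**Simulation of the same contrast** (6,000 runs per setting, robust SEs).

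- Constant 0.5 SD gap: power 73.1% without site, 73.6% with.
- 0.5 SD gap at follow-up: 71.2% and 74.1%.
- 1.0 SD gap at follow-up: 64.5% and 73.4%. Mean SE was 0.260 without site against an empirical 0.236 (10% too wide) and 0.230 with site. Null rejection was 3.2% and 5.6%.

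**Which term is needed.** GEE fits on the score scale (SD 1.84, three visits, 300 runs) gave these mean SEs for group-by-time at month 6:

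- Constant 1 SD gap: 0.427 without site and 0.427 with a site main effect. With dropout of 3 and 6 patients: 0.447 and 0.446.
- 1 SD site shift in change: 0.476 without site, 0.476 with a site main effect, 0.422 with site-by-time.

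So a site main effect alone does not help this contrast.

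**Group levels at one visit.** With within-site SD 1 the arithmetic is the same as in the table, but a constant gap now counts. For a constant 0.5 SD gap, simulated power for a follow-up-only comparison was 71.7% without site and 74.3% with. In general, if site explains a share R² of variance, the SE is too wide by 1/√(1 − R²): 1.005, 1.054 and 1.195 for R² of 1%, 10% and 30%. Take an effect that would give nominal 80% power using the total SD. True power without site is then Φ(0.8416/√(1 − R²)), and with site Φ(2.8016/√(1 − R²) − 1.96). The results are 80.1% → 80.4%, 81.2% → 84.0% and 84.3% → 91.8%.

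**Unequal sites.** For a 1.0 SD follow-up gap, 20,000 runs gave 66.9% → 73.6% with a 75/25 split and 69.6% → 73.4% with a 90/10 split.

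**Calibration of the adjusted test.** The uncorrected robust SE with site averages 0.230 against a true 0.236. Scaling by √(72/69), for 72 patients and three parameters in the change model, gives 0.230 × 1.0215 = 0.235.

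**The case against.** The strongest reply is that the omission may cost almost nothing. Baseline is one of the three visits, so group-by-time is the natural efficacy term, and a stable difference between hospitals cancels there. A reader might infer that power is lost whenever outcomes differ by site. The documents and the arithmetic do not support that for this term, because the two sites must change differently over time. Nothing in the documents shows that they do. A 1.0 SD divergence is larger than the assumed treatment effect, and the site split is not given.

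The second reply is that part of the simulated gain at a moderate gap comes from a slightly liberal adjusted test. This stands. With a 0.5 SD follow-up gap, 20,000 runs gave null rejection of 5.0% without site and 5.9% with it. The good calibration without site arises because two errors offset: the site variation left in the SE widens it, and the small-sample shortfall of the robust SE narrows it. In closed form the gain is 2 points rather than 3.

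The reply does not dispose of the point. The documents do not name the efficacy coefficient, and the Outcome Measure Template reports adherence as a single score per arm. Group-level comparisons, where a constant gap does cost power, are therefore not excluded.

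A reader might also infer bias or false positives. Neither follows: allocation was balanced by site, and the error is in the conservative direction.

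**Conclusion.** The point holds in limited form. Site governed allocation and is absent from the only stated model. The consequence is an SE that is somewhat too wide, for level comparisons when levels differ by site and for group-by-time only when changes differ by site.

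For the change contrast the power at stake is about 0 points (constant gap), about 3 points (0.5 SD at follow-up; 2 in closed form) and about 8 points (1.0 SD, a large gap). It is about 4 points at 1.0 SD if one site holds only a tenth of the patients. These figures rest on the assumed correlation of 0.5, effect of 0.6 SD, complete data and, except in the last case, equal sites. The actual loss cannot be determined from the documents. This is a modest, inexpensive improvement and gives no reason to doubt the validity of the comparison.

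**What to change.** Name the efficacy contrast. For every outcome, add site and site-by-time to the existing group, time and group-by-time terms, or justify leaving them out. Use a small-sample correction to the robust standard errors, for example degrees-of-freedom scaling with a t reference distribution, and state it with the model.

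The cost is one model statement, using a variable that the allocation already required, and up to three degrees of freedom (one for site, two for site-by-time). Without the correction there is a further cost: a test that rejects about 5.6 to 6% under the null. If the sites do not differ, almost nothing changes.

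Because the document already contains results, report a site-adjusted rerun as an analysis added later, beside the stated model.

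### The results form marks the adherence comparison as Equivalence with no margin, against the protocol's efficacy aim, and its boxed test method is not the stated GEE

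*Combined protocol and SAP*

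**What the plan says.** **Study Protocol.** The PURPOSE paragraph sets out to investigate efficacy on medication adherence, with knowledge, support, beliefs and self-efficacy as mediators. METHODS gives the schedule: "Data were collected at baseline, third month, and sixth month in both groups". DATA ANALYSIS says "The generalized estimating equations were used to analyze the efficacy of the intervention for enhancing knowledge", and the list of outcomes that follows ends with "self-efficacy, and adherence to anticoagulant therapies in patients treated with oral anticoagulants for atrial fibrillation".

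**Outcome Measure Template and its Statistical Analysis Template (adherence).**
- Type of test: Equivalence is boxed. Superiority is offered in the same list and is not boxed.
- The comment row keyed to footnote 3 is empty. Footnote 3 reads "If a non-inferiority or equivalence analysis, information on the definition of the non-inferiority or equivalence margin is required".
- P-value: 0.05, in a field whose printed instruction is "calculated value, not the a priori threshold for statistical significance".
- Method: the boxed option prints as F-Test, 2-Sided. The Other option has nothing entered.
- Estimation parameter: GEE has been typed into the list of options, which now reads "Median Difference (Net) (generalized estimating equation) Odds Ratio (OR".
- Estimated value: 0.5. A two-sided 95% interval is indicated, but both limits are blank.
- Other Statistical Analysis: a GEE was "used to model each outcome variable as a function of group effect, time effect, and group by time interaction effect".

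**The concern.** The type of test fixes what a p-value means. Under a superiority null, a small p-value is evidence that the arms differ. Under an equivalence null, it is evidence that they are similar to within a margin. The form labels the comparison as the second kind, while the protocol describes the first. An equivalence claim also has no content until a margin is stated, and none is.

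The method entry adds a second inconsistency. One p-value and one estimate sit beside a boxed classical test and a described GEE. Someone relying on the form cannot tell which of the two produced 0.05 and 0.5, or which contrast they describe. PURPOSE names adherence as the outcome, and it is the only outcome with a completed statistical entry in these documents, so this record matters.

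**Working it through.** **1. Text comparison.** The plan states no margin, alpha, power or sample-size derivation, so there is no planned figure to reproduce. The finding rests on setting the entries side by side.

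| Item | Study Protocol | Results form |
|---|---|---|
| Hypothesis | Efficacy (PURPOSE, DATA ANALYSIS) | Equivalence boxed |
| Margin | None | None; comment row blank, though footnote 3 requires one |
| Method | GEE | F-Test, 2-Sided boxed; GEE typed under the estimation parameter and described under Other Statistical Analysis |
| Result | Not given | p 0.05, estimate 0.5, limits blank |

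The conflict is between Equivalence and the efficacy aim, together with the missing margin. Neither a GEE nor a two-sided 95% interval is incompatible with equivalence in itself.

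**2. Illustration from the printed scores.** This does not come from the GEE.

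Inputs: intervention 8.1 and 1.4, control 9.2 and 2.2, with 36 analysed per arm (Outcome Measure Template). Completers are 33 and 30 (Participant Flow Template). Assumption: each pair is a mean and an SD. The form does not say which visit the scores refer to.

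At 36 per arm:
- Difference, intervention minus control: 8.1 - 9.2 = -1.10.
- SE = sqrt(1.4²/36 + 2.2²/36) = 0.4346.
- t = -1.10/0.4346 = -2.531. The Welch df is 59.4 and p = 0.0140.
- 95% CI: -1.97 to -0.23. 90% CI: -1.83 to -0.37.
- Pooled test: F(1,70) = t² = 6.41, p = 0.0136. A two-sided pooled t-test gives the same p, so it does not matter here whether the label is F or t.

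At 33 and 30:
- Pooled F(1,61) = 5.71, p = 0.020.
- Welch SE = sqrt(1.4²/33 + 2.2²/30) = 0.4698, df 48.3, p = 0.023. 90% CI: -1.89 to -0.31.

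**3. What each hypothesis would conclude.** On these values a superiority test shows a difference. Equivalence by two one-sided tests at 0.05 needs the 90% interval to lie inside the margin. The margin would have to exceed about 1.83 points at 36 per arm, or about 1.89 at 33 and 30. For scale, the pooled SD at 36 per arm is sqrt((1.4² + 2.2²)/2) = 1.84. With assumed margins at 36 per arm, the equivalence p-value is 0.59 for 1.0 point, 0.18 for 1.5 and 0.021 for 2.0. The two labels can therefore lead to different conclusions from the same numbers.

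**The case against.** The strongest reply is that this is a mislabelled form field and nothing more. An equivalence test cannot be computed without a margin, and both the protocol and the GEE description point to a test of difference. That is largely right. A reader might infer that the trial was designed or analysed as an equivalence trial. The documents do not support this, and a slip in completing the form is the likelier explanation. What stands is that the recorded hypothesis type contradicts the protocol and the form's own margin rule.

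A second reply concerns extraction. The boxes were read from a PDF, and several other lists on the form show no selection. The method label follows *t-Test, 1-Sided* in the list, so it may really be *t-Test, 2-Sided*. It would be wrong to insist that an F-test was used. The mismatch survives, because neither test is a GEE. The same box picks out exactly one option in each of three lists (test type, method and sides of the interval), which looks deliberate.

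Third, it is tempting to infer that 0.05 and 0.5 are wrong because the simple test gives about 0.014 and -1.10. That does not follow. The entries may come from a GEE coefficient, the 0.05 may be a significance threshold entered in the wrong place, and the parameter behind 0.5 is not identified.

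Fourth, footnote 4 says: "If the statistical analysis cannot be submitted using the Statistical Test of Hypothesis or Method of Estimation options, provide a description and the results". This does not forbid filling in the standard fields as well, so completing both is not a breach.

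Finally, one might say that no visit is selected. The form's time frame and analysis population both refer to 24 weeks, which points to the final visit.

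**Conclusion.** The point holds as an inconsistency that should be corrected, not as evidence of a faulty analysis. As extracted, the form records Equivalence for the adherence outcome with no margin, against a stated efficacy aim, and it boxes a method other than the GEE named in the protocol and on the form. The origin of p = 0.05 and of the estimate 0.5 is unclear, and no limits accompany them.

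The size of the effect on the trial's conclusion cannot be determined from the documents. The illustration shows only that the label matters: the printed values indicate a difference of -1.10 points, and they would support equivalence only with a margin above about 1.83 points. It assumes that the pairs are means and SDs, uses 36 per arm, and ignores the repeated measures. The finding on test type assumes that the extracted box reflects the mark on the original form, which can be confirmed by looking at it.

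**What to change.** 1. Change the type of test to Superiority, in line with PURPOSE and DATA ANALYSIS. If equivalence was truly intended, state the margin and when it was set.
2. Before changing the method entry, establish which analysis and which contrast produced 0.05 and 0.5. Relabelling them as GEE without this check could introduce a new error if they came from the boxed test.
3. Then enter GEE under Other as the method. Report the GEE group-by-time estimate at the 24-week time point with its own 95% limits and p-value, and replace any entry that did not come from the GEE. The month 3 contrast may be added.

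The cost is a few form entries (test type, method, estimate, limits, p-value and a comment line) and at most one rerun of the GEE on existing data. No new participants or data are needed.

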**Other (Not Including Serious) Adverse Events Template**

* § Time Frame		non applicable	
[*] Adverse Event Reporting Description			
Source Vocabulary Name for Table Default ①			
* § Collection Approach for Table Default ①		(Select One)	Systematic      Non-Systematic

* Army/Group Title		
* § Army/Group Description ②		

* Other (Not Including Serious) Adverse Events													
* Adverse Event Term	* Organ System	* Frequency Threshold for Reporting Other Adverse Events (0–5%)		* Number Participants Affected	* Number Participants at Risk	Number Events	* Number Participants Affected	* Number Participants at Risk	Number Events	* Number Participants Affected	* Number Participants at Risk	Number Events	
		_____ %	* Total										
		③			④ [*]			④ [*]			④ [*]		④ [*]
		③			④ [*]			④ [*]			④ [*]		④ [*]
		③			④ [*]			④ [*]			④ [*]		④ [*]
		③			④ [*]			④ [*]			④ [*]		④ [*]
		③			④ [*]			④ [*]			④ [*]		④ [*]
		③			④ [*]			④ [*]			④ [*]		④ [*]
		③			④ [*]			④ [*]			④ [*]		④ [*]
		③			④ [*]			④ [*]			④ [*]		④ [*]
		③			④ [*]			④ [*]			④ [*]		④ [*]
		③			④ [*]			④ [*]			④ [*]		④ [*]
		③			④ [*]			④ [*]			④ [*]		④ [*]
		③			④ [*]			④ [*]			④ [*]		④ [*]
		③			④ [*]			④ [*]			④ [*]		④ [*]

\* Required      \* § Required if Primary Completion Date is on or after January 18, 2017      [\*] Conditionally required

① If entered, the table default values apply to all Adverse Event Terms. The values may be changed for any single Adverse Event, if different from the table default.

② Arm/Group Description describes details about the intervention strategy (e.g., dose, dosage form, frequency, duration) or groups evaluated.

③ Organ System must be selected from a pick-list of high-level categories. See the Results Data Element Definitions for details.

④ Number of Participants at Risk for an Adverse Event Term is only required when the value differs from the Total Number of Participants at Risk.
